## 2. STUDY AIMS

The primary study objectives are as follows:

**Aim 1: Establish the feasibility of using mobile phones to follow up on hospitalized trauma patients after discharge in Cameroon.**

*Hypothesis:* Mobile phones are a feasible way of contacting trauma patients after they are discharged from the hospital in Cameroon.

We will contact trauma patients discharged from four hospitals participating in the Cameroon National Trauma Registry at intervals of two weeks, one month, three months, and six months following discharge. The response rate and decay of response over time will be tracked.

**Aim 2: Cross-validate a telephone-based triage tool to identify trauma patients who would benefit from further medical care.**

*Hypothesis:* A triage tool administered over the telephone can effectively identify injured patients who would benefit from further care for their injuries.

An over-the-phone triage tool will be used to predict a binary outcome two-weeks after discharge: needs further care or does not need further care. An independent physician blinded to triage tool outcome who will also render a determination on the same binary outcome, will examine those patients contacted by telephone. Physician assessment will be used as the gold standard to calibrate the model, which will be validated in a separate patient cohort.

**Aim 3: Characterize the impact of timely follow-up on long-term disability and socioeconomic consequences associated with trauma in Cameroon.**

*Hypothesis:* Trauma patients in need of post-hospitalization medical care will have improved disability outcomes if follow-up care is delivered promptly.

Patients will be given a modified Glasgow Outcomes Scale-Extended (GOSE) survey to complete at two weeks, one month, three months, and six months after hospitalization to quantify the death and disability associated with traumatic injury for each patient. Pre- and post-intervention results will be compared.

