## Primary Outcomes

mHealth triage tool score; physician exam determination for “needs further care” or “does not need further care”.

**Sample Size:** The preliminary triage instrument has 13 variables derived from 7 questions. A minimum sample size of 10 participants per variable per potential model outcome (either needing further care or not needing care) is required to adequately power regression analysis. Our preliminary data suggests that physician exams leading to a recommendation for further care occur for 13.7% of calls. Conservatively estimating that 10% of contacted patients will require further care, a sample size of 1300 patients in the triage cohort will be targeted.

**Data Analysis:** Data from the prospective cohort will be divided into training and validation groups (70% and 30% of the overall cohort respectively). Stepwise multiple regression with bidirectional elimination will be used on the training group dataset to build the best model for predicting physician recommendation for further care (considered as a binary outcome). Survey questions that are found not to contribute significantly to prediction will be dropped from the final triage tool. The resultant model will be applied to data from the validation cohort. To establish predictive accuracy, we will assess calibration of the model by comparing the mean error between the predicted risk and actual physician response in this cohort. Receiver operating characteristic (ROC) curves will be calculated to evaluate the discrimination of the model. As the consequences of a false-positive survey leading to unnecessary patient follow-up are minimal, whereas false-negatives may result in poor health outcomes, risk cutoffs will target a highly sensitive test with minimal false negatives. Ratings of telephone follow-up acceptability will be aggregated and summarized.

**Aim 3: Characterize the impact of timely follow-up on long-term disability and socioeconomic consequences associated with trauma in Cameroon.**

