*Supplement Sample Size Calculations Adjustment:* Data collected from our prospective cohort will be divided into training and validation groups (70% and 30% of the overall cohort respectively). Our original sample size was calculated to account for a conservative prevalence of 10% of contacted patients needing further follow-up care. Based upon detecting a significant departure from 50% specificity, we estimate that we would require approximately 400 patients who are not recommended for follow-up care to be included in our validation sample. We will therefore target a sample size of 1330 trauma patients in our triage cohort. New multicenter preliminary data, however, suggest that physician exams leading to a recommendation for further care occur for 50% of contacted patients. This is a significant deviation from prior single-institution Cameroon pilot data that estimated 13.7% of contacted trauma patients would need further care. The inclusion of additional hospital sites that receive patients with more severe injuries as well as selection bias are likely contributing to this difference. If our preliminary findings remain consistent, we anticipate only requiring 220 patients not recommended for follow-up care to be included in our validation sample and 730 patients to be targeted in our triage cohort. Using a conservative estimate for our sample size calculation approach enables us to create a buffer and ensure our study is adequately powered to achieve statistical significance.

Triage tool was administered at 2 weeks with physician examination assessments from February 2020 till August 2022 (with the pauses noted above). Final 2 weeks follow-up was completed on September 14, 2022.

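### The only calibration measure planned for the Aim 2 model is the mean error, which checks the overall level of risk but not whether predicted risks are too extreme or too flat

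*Combined protocol and SAP*

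**What the plan says.** The Data Analysis paragraph under Primary Outcomes (Section 3A, Aim 2) builds and checks the model in these steps:

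- Split: "Data from the prospective cohort will be divided into training and validation groups (70% and 30% of the overall cohort respectively"). The Addendum repeats the 70/30 split and adds no performance measure. Neither place says how patients are allocated. Section 2 describes the arrangement differently: "Physician assessment will be used as the gold standard to calibrate the model, which will be validated in a separate patient cohort".
- Model: "Stepwise multiple regression with bidirectional elimination will be used on the training group dataset to build the best model". The outcome is the physician's binary determination. Selection starts from 13 candidate variables ("The preliminary triage instrument has 13 variables derived from 7 questions"), and no shrinkage is mentioned.
- Calibration: "we will assess calibration of the model by comparing the mean error between the predicted risk and actual physician response in this cohort". Whether the error is signed, absolute or squared is not stated.
- Discrimination: "Receiver operating characteristic (ROC) curves will be calculated to evaluate the discrimination of the model".
- Use: "risk cutoffs will target a highly sensitive test with minimal false negatives".

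No calibration slope, calibration plot, grouped comparison of observed with expected, Brier score or acceptance limit appears anywhere in the document.

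**The concern.** A regression with an intercept, whether logistic or least squares, makes the mean predicted risk equal the observed rate in the data it was fitted to. If the validation group is a random part of the same cohort, the expected signed mean error there is about zero whatever the predictors contribute. The check therefore says little about the fault most likely here. Stepwise selection without shrinkage tends to give risks that are too extreme: too low at the low end and too high at the high end. These errors cancel in the average.

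What is at stake is the meaning of the calibration result. The study is powered for Aim 2, and a near-zero mean error could be reported as good calibration when the risks are mis-scaled. That matters to anyone who uses the predicted risks themselves, or who sets a threshold at a stated risk.

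**Working it through.** **1. Sizes, from the plan's own figures.** Original target: 10 participants × 13 variables / 0.10 = 1300, as stated. Addendum: 400 / 0.30 = 1333 (stated as 1330) and 220 / 0.30 = 733 (stated as 730). The 30% validation groups are 390, 399 and 219 patients. At 10% prevalence, 390 patients give 0.10 × 390 = 39 events.

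**2. Sampling error of the signed mean error in a random split.** The standard error is about √[p(1−p)(1/n_val + 1/n_train)].

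- 1300 patients, 10%: √[0.09 × (1/390 + 1/910)] = 0.018.
- 730 patients, 50%: √[0.25 × (1/219 + 1/511)] = 0.040.

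The expected value is about zero in both cases.

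**3. Simulation.** The document gives no effect sizes, item frequencies or selection thresholds, so these are assumptions: 13 yes/no items at 30% frequency, five with a true log odds ratio of 0.4 (weaker) or 0.8 (stronger), entry at p<0.05, removal at p>0.10, a random 70/30 split and 150 repetitions. Error is predicted minus observed.

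| Scenario | Mean error, stepwise (SD) | Mean error, no predictors | Median slope, stepwise | AUC, stepwise |
|---|---|---|---|---|
| 1300, 10%, weaker | 0.0005 (0.0205) | 0.0003 | 0.47 | 0.56 |
| 1300, 10%, stronger | 0.0009 (0.0183) | 0.0007 | 0.88 | 0.70 |
| 730, 50%, weaker | -0.0030 (0.0432) | -0.0029 | 0.66 | 0.57 |
| 730, 50%, stronger | -0.0007 (0.0404) | 0.0005 | 0.87 | 0.68 |

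The mean error barely separates a stepwise model from an empty one, although the slopes are below 1.

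**4. The three readings of mean error** (1300 patients, 10%, stronger effects). The doubled and halved models are artificial. Their intercepts were re-set so that the training mean still matched.

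| Model | Signed | Absolute | Squared | Median slope | AUC |
|---|---|---|---|---|---|
| Stepwise | 0.0009 | 0.167 | 0.085 | 0.88 | 0.70 |
| No predictors | 0.0007 | 0.179 | 0.089 | not defined | 0.50 |
| Log-odds doubled | 0.0011 | 0.158 | 0.092 | 0.44 | 0.70 |
| Log-odds halved | 0.0008 | 0.173 | 0.085 | 1.75 | 0.70 |

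The absolute error is lowest for the over-extreme model. The squared error is dominated by the outcome variance (0.10 × 0.90 = 0.09) and does not separate the stepwise model from the halved one. The AUC is identical for the stepwise, doubled and halved models.

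**5. What a slope does to a low risk.** Take the scale as pivoting at the 10% mean (an approximation). A predicted 3% has log-odds -3.476, which is 1.279 below the -2.197 of 10%.

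- Slope 0.88: -2.197 − 0.88 × 1.279 = -3.323, a true risk of 3.5%.
- Slope 0.47: -2.197 − 0.47 × 1.279 = -2.798, a true risk of 5.7%.

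**6. Shift in level.** When the hold-out had its log-odds of need raised by 0.6, as a different site or period might, the signed mean error was -0.06 (10%) to -0.14 (50%). A simple z-test flagged it in 95% to 99% of runs. That test ignores training-sample error and also flagged 11% to 17% of unshifted stepwise runs. Even against the fuller standard errors in step 2 the shift stands out: 0.0596/0.018 and 0.1282/0.040 are both above 3.

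**7. Effect on sensitivity.** The cut-off was set in training to reach at least 90% sensitivity. Mean sensitivity, training to validation:

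| Scenario | Weaker effects | Stronger effects |
|---|---|---|
| 1300, 10% | 0.982 to 0.968 | 0.931 to 0.909 |
| 1330, 50% | 0.978 to 0.973 | 0.923 to 0.922 |
| 730, 50% | 0.985 to 0.978 | 0.929 to 0.920 |

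The largest fall is 0.931 − 0.909 = 0.022. A further set of 60 runs per scenario gave at most about 3 percentage points.

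**The case against.** Four arguments can be made for the plan as written.

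First, a reader might infer that the mean error can reveal nothing wrong with the risks. That goes too far. It detects a wrong overall level (step 6). The split is not stated to be random, and Section 2 speaks of a separate cohort. The Addendum's move from 13.7% to 50% needing care shows that the level can change between settings. This stands, but even then the measure says nothing about error across the risk range.

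Second, a reader might infer that a model with no useful questions would pass validation. It would not: the ROC curve planned in the next sentence would give an AUC of 0.5. This stands. The gap is limited to mis-scaled risks, which leave ranks unchanged.

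Third, a reader might infer that undetected overfitting will produce the missed patients that the plan wants to avoid. The text does not support this. The cut-off is to be chosen for high sensitivity, and no fixed risk value is given. Rescaling the log-odds leaves the same patients above such a cut-off, and step 7 shows only a small loss. This stands unless a threshold is set on the absolute risk scale, which the plan does not rule out.

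Fourth, the alternative is itself imprecise. In the simulations the slope's 95% interval excluded 1 in only 11% to 37% of runs. This stands too, and it limits what the change can deliver.

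**Conclusion.** The concern holds in a limited form. The one calibration measure in the plan, on its natural signed reading in a random hold-out, can test only calibration-in-the-large. It cannot show risks that are too extreme or too flat, and the ROC curve does not fill that gap. On the absolute or squared reading it is not a clean calibration measure.

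Under the assumed effects the stepwise model's median slope is about 0.5 to 0.9 while the mean error averages within 0.003 of zero. The slope values depend on the assumed effects. The near-zero mean error does not: it follows from fitting an intercept and splitting at random, and it would not hold for a split by site or period.

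The consequence is an uninformative calibration claim for reported risks and for any cut-off set at a stated risk. It is not a demonstrated rise in false negatives. The remedy improves what is reported and does not add a strong test.

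**What to change.** Replace the calibration sentence in the Aim 2 Data Analysis paragraph with:

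> Calibration in the validation group will be assessed by the calibration slope (logistic regression of the physician determination on the log-odds of predicted risk) and the calibration intercept (the same regression with that term as an offset), each with a 95% confidence interval, and by a smoothed calibration curve covering the range around the cut-off. The signed mean error (mean predicted minus observed) will be reported as calibration-in-the-large only.

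In the same paragraph, state how the 70/30 split is made (at random, by site or by period) and bring the description of the validation group in Section 2 into line with it.

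The cost is a few lines of text and code, with no new patients or data. The calibration result may look less favourable than a near-zero mean error. With about 39 validation events at 10% prevalence the slope will be imprecise, so it should be given as an estimate with its interval and not used as a pass/fail criterion.

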**mHealth telephone triage tool:** Our community-based survey found that 95% of respondents had access to a cell phone in their household. Cell phone numbers are also routinely collected as part of the multi-institutional trauma registry's patient demographic data. Pilot data from the 3-site trauma registry suggests that about 57% of urban and 70% of rural households have cellphone access, and 54% of patients overall were willing to provide cell phone numbers for healthcare follow-up after injury. Preliminary testing was done to identify the best method of calling participants that yields the highest response rate. To test the hypothesis that patient-initiated follow-up would vary by time from discharge, we retrospectively identified patients at 3 contact points post-discharge from the hospital (3, 6, and 12 months) and called them during the same 2-week period. During these calls, participants answered the Glasgow Outcomes Score Extended (GOSE) survey. In data collected for 331 patients, 64% of cell phone numbers provided were reached and 39% of subjects or families participated in surveys. Contact rates were slightly higher for patients contacted at 3 months post-discharge (68%) than for those contacted at 6 months (61%) and 1 year (58%), but survey completion rates at all 3 time points were similar. Call outcomes when surveys were not done included failure of the respondent to

know the patient (37%), phone disconnection (29%), and no answer (26%). There were no significant differences in the distribution of non-response by contact time-point.

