## APPROACH

**Aim 1: Establish the feasibility of using mobile phones to follow up on hospitalized trauma patients after discharge in Cameroon.** This aim will be addressed through a prospective cohort study following discharged trauma patients longitudinally over 6 months. The following data will be extracted from the existing trauma registry: patient demographics, clinical course, injury severity, disposition, and patient cell phone numbers. All admitted trauma patients who provided cell phone numbers in the emergency department will be contacted at intervals of 2 weeks and 1, 3, and 6 months post-discharge. Contact points at 2 weeks and 1 month correspond with traditional post-injury follow-up visits when intervention is theoretically likely to positively impact patient trajectory. These time points have also been used in prior mobile-health follow-up studies in traumatic brain injury and surgical patients in developed settings. Three and 6-month time points were selected because our preliminary data showed higher rates of disability and survey response at 3 and 6 months than at 12 months. Attempts will be made to contact patients at least 3 times by calling and once by text message over a 1-week interval at each time point.

**Outcomes:** number and proportion of successful attempts.

[figure not shown]
**Sample Size:** This overall study is powered for Aim 2 (see below), but the study population for Aim 2 will be used to calculate the number and proportion of successful attempts in Aim 1.

**Data Analysis:** Feasibility will be assessed through calculation of the number of successful contacts; number of attempts required to achieve success; cost associated with personnel and telephone time; reason for contact failure; and survey administration time. Frequencies and proportions of successful contacts will be calculated for each time interval and temporal trends will be described. Mean and standard deviation for personnel time and call cost will be used to calculate average cost per patient contact and determine the overall feasibility of cell phone interviewing as a follow-up method.

**Aim 2: Cross-validate a telephone-based triage tool to identify trauma patients who would benefit from further medical care.**

**Study design:** The 4 hospitals will start in a stepped wedge design the implementation of mHealth telephone triage tool (see Figure 1).

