**Implementation/Data Collection:** Patients contacted two weeks after discharge will be asked to give additional consent for participating in the triage tool part of the study. Those who consent will be contacted by research assistants and will answer 7-question survey. Patients whose responses trigger concern about the need for further medical attention will be informed that they should return to care and given appropriate instructions. All patients, regardless of triaged status, will be asked to schedule a time for a physical exam and will undergo one either at the hospital or in their place of residence. If patients return to the hospital, compensation for travel expenses will be provided on a sliding scale. This exam will occur within 1 week of the phone interview. Trained study physicians will conduct a structured, standardized exam that will ultimately culminate in a dichotomous outcome for “needs further care” or “does not need further care”. Based on the exam, the physician will determine if the patient would benefit from further services (including additional follow-up care, diagnostic or therapeutic interventions). Additional data will be collected regarding physician opinion as to whether the patient is demonstrating on-trajectory recovery for their age, health status, and injury, and whether the patient is at high, moderate, or low risk for a poor outcome. At the 2-week and 6-month time points, all contacted patients will be asked about their satisfaction with formal medical services, post-injury follow-up care, perceived convenience, and utility of mobile telephone follow-up.

**Figure 1: Step-wedge design of study.** For each site: Diagonal lines depict a GOSE baseline data collection phase, gray arrows depict intervention phase (1 year/site), and black blocks depict follow-up phase (6 months/site).

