**Implementation/Data Collection:** Injured patients who are successfully contacted at any of the study time points following hospital discharge will answer an over-the-phone survey to assess disability using an augmented GOSE (aGOSE) instrument, which is a metric of multi-domain functional status initially targeted for patients following neurologic trauma. It has since been validated in diverse geographic locations and in broader clinical contexts. Additional questions to evaluate economic consequences of injury will be added to the existing GOSE instrument. As our preliminary experience indicates that respondents are extremely reticent to speak directly about money over the phone, indirect measures of economic consequences will be emphasized (**Table**). Respondents will also be asked whether they sought further care for their injuries and if so, whether care was rendered. Six months before we begin using the telephone triage tool we will collect baseline data at all 4 facilities, after which the triage tool will be implemented in a stepped-wedge fashion in the 4 facilities, staggered by three months for each facility's start date. The cohort of patients (or their surrogates) who answer the triage survey will also be asked to answer the aGOSE, which will be administered at 2-weeks and at 1, 3, and 6 months. This design will let us compare intervention patients with historical controls, while controlling for temporal trends.

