### **INFORMED CONSENT**

We have been collecting trauma registry data in Cameroon since 2008 in collaboration with the Ministry of Public Health. The protocol was reviewed and approved by the Cameroonian Ministry of Public Health, the National Ethics Review Committee in Cameroon, and the Institutional Review Board of the University of California, Los Angeles. Data collection is performed 24 hours per day and seven days per week. After obtaining patients' oral consent, trained staff at each of the four hospital sites collect all relevant information on trauma registry forms, which has a check box to ensure oral consent was given by the patients. At this time, trauma patients are also asked for household mobile phone numbers. If a trauma patient is a child under the age of 21, the mobile phone number of one of her/his parent(s) or guardian(s) is obtained. Where clinically possible, patients are reassured that mobile phone numbers, are being collected for research purposes only.

Two weeks after each trauma patient is discharged, the patient's household is contacted by trained research staff and invited to participate in the study. Consent for participation is obtained orally, over the phone. During this oral consent process, trained research assistants inform potential participants about the purpose of the research, the potential benefits and risks that are involved, and how potential risks are minimized. Potential participants are strongly encouraged to ask questions and have the research staff clarify any information that is not clear. If oral consent is received from the trauma patient or their caregiver the research assistant indicates this by checking a box on the triage tool. To consent to study participation, subjects or caregivers must be over the age of 21 and demonstrate understanding of the study. Households who decline consent are thanked for their time and no further contact is made. All households, regardless of consent status are offered the telephone number of the Cameroon-based Program Manager in the event that they have further questions or comments.

The request for consent as well as any study questionnaires is delivered in the subjects' primary language, either English or French. All research assistants are fluent in both English and French.

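### Aim 3 compares phone respondents only, and its exposure, triage-tool contact, is itself a response behaviour: define cohorts by period and examine non-response

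*Combined protocol and SAP*

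**What the plan says.** Aim 3 outcomes are collected by telephone. Under Aim 3, Implementation/Data Collection: "Injured patients who are successfully contacted at any of the study time points following hospital discharge will answer an over-the-phone survey". Respondents are also asked whether they sought further care, which is the aim's primary outcome. The same paragraph says of the triage patients: "The cohort of patients (or their surrogates) who answer the triage survey will also be asked to answer the aGOSE". How a patient comes to answer the triage survey is set out under Aim 2, Implementation/Data Collection: "Patients contacted two weeks after discharge will be asked to give additional consent for participating in the triage tool part of the study".

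The general calling rule, under Aim 1 in Approach, is wider: "All admitted trauma patients who provided cell phone numbers in the emergency department will be contacted at intervals of 2 weeks", and again at 1, 3 and 6 months. The Informed Consent section describes a two-week telephone invitation to the study and adds: "Households who decline consent are thanked for their time and no further contact is made". It does not say whether this applied in the baseline phase.

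Aim 3 Data Analysis compares the baseline and intervention cohorts by Kruskal-Wallis and chi-square tests. It then fits univariate and adjusted regressions with triage-tool contact as the predictor of GOSE level, economic disability and presentation for follow-up. The covariates listed for the GOSE model are site, severity, mechanism, age and gender. The logistic models are called adjusted without a list; I take the same list to apply.

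The registry data extracted for the study are "patient demographics, clinical course, injury severity, disposition, and patient cell phone numbers". No section defines an Aim 3 analysis set, a missing-data method, a comparison of respondents with non-respondents, or weighting for response.

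**The concern.** Answering a call two weeks after discharge and agreeing to a further survey is behaviour that may well be related to recovery and to care seeking. When that behaviour defines the exposure, part of any difference may reflect who cooperates rather than what the tool does.

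The Addendum makes this matter more. The stepped wedge, which was to control temporal trends, was abandoned, and data collection was suspended from April to September 2020. What remains is largely a before-after comparison, in which a shift in who responds can look like an effect of the tool. The Addendum's sample-size adjustment itself names selection bias, alongside more severe case mix at added sites, as a likely reason why 50% rather than 13.7% of contacted patients were judged to need further care.

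Aim 3 Data Analysis intends the results to supply an effect size for a future validation study. A biased estimate would pass into that study's design. Calling the aim exploratory excuses low power, not bias.

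**Working it through.** **The plan's own figures.** Aim 3 states no sample size, response target or effect size, so there is none to reproduce. The powered figure belongs to Aim 2 and reproduces: 10 × 13 / 0.10 = 1300. It is not disputed. On response, the mHealth telephone triage tool section reports: "In data collected for 331 patients, 64% of cell phone numbers provided were reached and 39% of subjects or families participated in surveys". That is about 331 × 0.64 = 212 numbers reached and 331 × 0.39 = 129 surveys.

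**Step 1: how far the two entry rules could differ.** Assume each call succeeds independently with probability p. Entry at any of four calls admits 1 − (1 − p)^4; entry at two weeks admits p.

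- p = 0.39: 1 − 0.61^4 = 0.862 against 0.39. Share of any-call entrants who fail the two-week rule: (0.862 − 0.39)/0.862 = 55%.
- p = 0.64: 1 − 0.36^4 = 0.983 against 0.64. Share: (0.983 − 0.64)/0.983 = 35%.

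Response correlated across calls would narrow this gap.

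**Step 2: spurious difference from the entry rules alone.** Assume two equal patient strata, with the same care seeking in both cohorts (no true effect) and a different response per call in each stratum. Baseline entry is by any of four calls; intervention entry is at two weeks only. The respondent proportion is (c0·y0 + c1·y1)/(c0 + c1), where c is the entry probability and y the care seeking in each stratum.

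| Response per call | Care seeking by stratum | Baseline | Intervention | Difference |
|---|---|---|---|---|
| 39%, 39% | 20%, 40% | 30.0% | 30.0% | 0 |
| 30%, 48% | 20%, 40% | 31.0% | 32.3% | 1.3 points |
| 24%, 54% | 20%, 40% | 31.8% | 33.8% | 2.1 points |
| 30%, 48% | 20%, 60% | 42.0% | 44.6% | 2.6 points |
| 24%, 54% | 20%, 60% | 43.6% | 47.7% | 4.1 points |

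Worked example, second row. Any-of-four entry is 1 − 0.70^4 = 0.760 and 1 − 0.52^4 = 0.927. Baseline is (0.760 × 0.20 + 0.927 × 0.40)/(0.760 + 0.927) = 31.0%. Intervention is (0.30 × 0.20 + 0.48 × 0.40)/0.78 = 32.3%.

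Weighting each stratum by its inverse entry probability returns the true 30% or 40% in both cohorts, provided that the registry records the stratum.

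**Step 3: selection directly on care seeking.** Assume true care seeking of 40%, with response r1 in seekers and r0 in non-seekers. The observed proportion is 0.40·r1/(0.40·r1 + 0.60·r0).

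- r1 = 0.45, r0 = 0.35: 0.18/0.39 = 46.2%, an excess of 6.2 points.
- r1 = 0.49, r0 = 0.32: 0.196/0.388 = 50.5%, an excess of 10.5 points.

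These become between-cohort differences only if the other cohort has no such selection. With the first pattern in one cohort and the second in the other, the difference is about 4 points. With the same pattern in both it is 0.

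**The case against.** **The baseline entry rule is inferred.** A reader might conclude that baseline patients demonstrably entered if reached at any of four calls. The documents do not say so. If the two-week consent in Informed Consent also governed baseline, the gap shrinks to the additional triage consent and to patients first reached after two weeks. The Protocol Summary also names the pre-intervention population as the control arm, so a period-based definition is partly present. This stands, and it is a reason to write both definitions down. It does not rescue triage-tool contact as an exposure.

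**Some selection is already handled.** A reader might say that the plan makes no use of registry data against selection. That is too strong. The adjusted models condition on five characteristics, outcomes are stratified by several factors, and self-reports are checked against records where possible (Limitations). But the chi-square, Kruskal-Wallis and univariate results have no such protection, and none of these measures defines who is analysed.

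**The pilot rate is a weak guide.** It comes from retrospective calls at 3, 6 and 12 months, made from an unrecognisable number. The protocol lists remedies and expects higher rates. This stands.

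**Weighting has limits.** If recorded variables do not predict care seeking, weights leave the 46% in Step 3 unchanged. This stands, and the fix has to say so. Nor does the registry describe everyone, because patients who refuse consent are excluded.

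**Conclusion.** The concern holds in this form: Aim 3 is a comparison among phone respondents, its regression exposure is a response behaviour that baseline patients could not show, and nothing in the plan addresses non-response beyond covariate adjustment in some of the models.

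The size and direction of the bias are unknown. About 1 to 4 points is what the entry rules alone produce under the assumed strata, response rates and independent calls; it is 0 when response does not vary between strata. A reader might infer a bias of 6 to 11 points. The documents do not support that figure, which needs selection on the outcome in one cohort only, whereas both cohorts are phone respondents and shared selection largely cancels.

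Aim 3 is exploratory and Aim 2 is unaffected. What is at risk is the interpretation of the Aim 3 effect estimates and their use in planning a later study.

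**What to change.** In Aim 3 Data Analysis:

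1. Define the baseline and intervention cohorts by discharge date relative to each site's actual tool start date, since the planned stagger was abandoned, and assign the COVID suspension period explicitly. Make this the main comparison. Include every patient reached in each period whether or not the triage survey was answered, and keep the triage-contact analysis as secondary. State the consent rule that applied in each period.
2. Compare respondents with non-respondents on registry data, by cohort and time point. Report a comparison weighted by the inverse probability of response, modelled within cohort from the extracted registry variables, beside the unweighted one. State the target population, including how patients who gave no phone number are treated.
3. State that weighting corrects only selection explained by recorded variables. Add a sensitivity analysis in which response depends on care seeking differently in the two cohorts.

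State also who was offered the aGOSE. The Addendum gives June 2021 as the end of new aGOSE recruitment, while triage ran to August 2022. Patients never offered the survey are not non-respondents, and weights cannot stand in for them.

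The cost is analysis programming on data already held, assuming that intervention-phase patients who did not answer the triage survey were still given the aGOSE when reached, as the protocol provides. Intervals will be somewhat wider, and a period-based comparison dilutes the effect among those actually reached. A joint mixed or GEE model for repeated GOSE is optional.
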